**15.4.5 Time to treatment failure up to Month 6**

The analysis of this endpoint will be performed using a two-sided stratified log-rank test, stratified by sex and ERT treatment status at screening. Kaplan-Meier estimates for the survival functions by treatment group will be plotted using Kaplan-Meier curves and will be tabulated by monthly intervals with their 95% CIs.

The treatment effect will be measured by means of a hazard ratio (and its 95% CI) calculated using a stratified Cox's proportional hazard model stratified by sex and ERT treatment status at screening.

This analysis will be implemented by the following SAS® code:

```
/* Kaplan Meier */
proc lifetest;
  strata treatment;
  id subjid;
  time time*censor(1);
run;

/* Stratified log-rank test */
proc lifetest;
  strata sex ertstatus / group = treatment;
  id subjid;
  time time*censor(1);
run;

/* Stratified Cox model */
proc phreg;
  class treatment (ref="placebo");
  model time*censor(1) = treatment / ties=exact rl;
  strata sex ertstatus;
run;
```

## 16 SAFETY ANALYSIS

### 16.1 Adverse events

All AEs and SAEs will be coded using the latest available version of MedDRA.

Analysis of AEs will be performed by counting subjects with a same MedDRA preferred term. Thus, a subject having experienced the same event (preferred term) more than once within the period of interest will be counted only once in the number of subjects with that event. A subject with several different events of the same SOC will be counted only once in the summary of events for each single SOC.

Summaries of AEs by treatment group will be presented by descending order of frequency in the active treatment group, i.e., SOC and preferred terms with the highest number of occurrences will appear first.

Treatment-emergent AEs will be summarized in a table by treatment group, SOC and preferred term displaying the total number of subjects exposed and the number (and percentage) of subjects reporting treatment-emergent AEs in total, by SOC and by preferred term within SOC.

Treatment-emergent AEs will also be summarized in a table by treatment group and preferred term.

The proportion of subjects who experienced treatment-emergent AEs will also be tabulated by SOC, preferred term, and maximal intensity. AEs with missing intensity will be considered as severe (the count of imputed AEs will be reported).

These 3 tables will be repeated counting only the treatment-emergent AEs (TEAEs) judged as related by the investigator.

Treatment-emergent SAEs and treatment-emergent SAEs judged as related by the investigator will be summarized similarly to TEAEs. A listing of all SAEs will be prepared on the SAF.

Treatment-emergent AEs leading to premature discontinuation of study treatment will be listed and summarized similarly to TEAEs.

For patients experiencing a treatment-emergent AE with fatal outcome, a summary table will present counts of patients by primary cause of death. A listing of all deaths will be prepared on the SCR.

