1.4 Summary of known and potential risks and benefits

The potential benefits of lucerastat administration, for subjects participating in this study, include a decrease (in frequency and/or intensity) of FD symptoms such as neuropathic pain, GI symptoms (diarrhea, constipation, abdominal pain), and an improvement of their QoL.

The potential risks for subjects participating in this study are related to those based on the nonclinical findings of the study treatment [see Section 1.2.2], discontinuation of ERT [see Section 5.2.3.1], and risks and discomforts associated with some of the study tests and procedures [see Section 7.2].

There is potential risk in both placebo and lucerastat treatment groups that FD symptoms or condition may not get better or may get worse. It should be noted that during the shortage of the ERT agalsidase beta supply between June 2009 and January 2012, no increase in clinical event incidence [Smid 2011] and only mild decrease in renal function [Weidemann 2014, Lenders 2016] could be observed in subjects with FD receiving a reduced dose of agalsidase beta.

In this study, the most invasive procedure repeated at each visit will be blood sampling. All test procedures (e.g., blood sampling, electrocardiogram [ECG], echocardiography) are part of the routine standard-of-care of subjects with FD, although their frequency may be higher in the study. The use of the electronic diary (eDiary) carries no to little risk to the subjects.

The following measures will contribute to minimize the risks for the subjects participating in the study, in particular those who discontinue ERT at screening:

- Exclusion of subjects at high risk of developing clinical signs of organ involvement within the time period of the study (as per investigator judgment), including subjects with substantial organ damage and severe complications of FD [see Section 4.4];
- Maintenance of the background pain medications such as anti-epileptics and TCAs [see Section 5.2.3.2];
- Individualized Pain Management Plan (IPMP) set up at the screening visit for each subject [see Section 5.2.3.2.2];

- Close follow-up of the subjects throughout the study with daily collection of symptoms via an eDiary and with four site visits scheduled during the 6-month treatment period [see Section 7.1];
- Monitoring of safety and efficacy data by an Independent Data Monitoring Committee (IDMC) [see Section 3.3.1];
- Study-specific criteria for stopping study treatment [see Section 5.1.10];

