3.1.1 Study periods

The study comprises the following consecutive periods:

Screening period: Lasts approximately 6–7 weeks; starts with the signing of the informed consent form (ICF; at the screening visit) and ends the day before subject randomization.

Treatment period: Lasts approximately 6 months. Starts on the day of subject randomization (randomization visit) and ends at the EOT visit (Month 6). It will consist of site visits at Month 1, Month 3, Month 5 and Month 6 and telephone call visits at Month 2 and Month 4.

The EOT visit will take place at Month 6 (or earlier in the event of premature discontinuation).

Whenever possible, the EOT visit should take place 1 day after the last dose of study treatment but no later than 7 days after the last dose of study treatment.

Post-treatment observation period (PTOP): Subjects who discontinue study treatment prematurely will enter into the PTOp, which starts on the day after the last dose of study treatment, and ends at latest at the Month 6 PTOp visit.

During this period, all assessments except PK will be performed. They will be performed at the time of the originally scheduled visits [[Table 6](#)].

Post-treatment safety follow-up (FU) period: The FU period is applicable to all subjects except those who enter the open-label extension (OLE) study. It starts on the day after the last dose of study treatment:

- For female and non-fertile male subjects: it includes 1 safety FU telephone call (FU1) taking place approximately 1 month after the last dose of study treatment;
- For fertile male subjects: it includes 2 safety FU telephone calls taking place approximately 1 month (FU1) and 3 months (FU2) after the last dose of study treatment.

Subjects who complete the 6-month double-blind treatment period will be proposed to enroll into an OLE study conducted under a separate protocol (provided the OLE study protocol has been approved in the country/site by regulatory authorities and Ethics Committees [ECs] / Institutional Review Boards [IRBs]).

Subjects who discontinue study treatment prematurely for any reason should be subsequently treated according to local standard-of-care at the investigator's discretion and will be followed in the PTOp until the originally scheduled Month 6 visit.

[figure not shown]
For an individual subject, the End-of-Study (EOS) is defined as follows:

- For subjects who enter the OLE study, the EOS corresponds to the EOT visit;

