4.3 Inclusion criteria

For inclusion in the study, the subject must fulfill all the following inclusion criteria at the specified study visits. It is not permitted to waive any of the criteria for any subject:

Screening visit criteria

1. Signed and dated ICF prior to any study-mandated procedure;
2. Male or female subjects 18 years old and above;

3. FD diagnosis confirmed with local genetic test results (i.e., presence of at least 1 mutation in *GLA*, the gene coding for α -GalA);
4. Fabry-associated neuropathic pain, as defined by the subject, in the last 3 months prior to screening;
5. ERT treatment status:
 - a) Subject never treated with ERT; or
 - b) Subject has not received ERT for at least 6 months prior to screening; or
 - c) Subject treated with ERT at the time of the screening visit, and meeting all of the following criteria at the time of screening:
 - i) ERT administration for the last 12 months;
 - ii) Stable ERT dose regimen during the last 3 months;
 - iii) Subject agrees to stop ERT administration at the screening visit for approximately 8 months (6–7 weeks screening + 6 months of double-blind treatment).
6. A woman of childbearing potential [see definition in Section 4.5.1] is eligible only if the following applies:
 - Negative serum pregnancy test at screening and a negative urine pregnancy test at randomization;
 - Agreement to undertake monthly urine pregnancy tests during the study and up to at least 30 days after study treatment discontinuation;
 - Agreement to follow a highly effective contraception scheme as described in Section 4.5.2 from screening up to at least 30 days after study treatment discontinuation.
7. A fertile male (physiologically capable of conceiving a child according to investigator judgment) who is sexually active with a woman of childbearing potential is eligible only if the following applies:
 - Agreement to use a condom during the treatment period (starting at randomization) and for up to 3 months after study treatment discontinuation; and
 - Agreement not to father a child during this period.

Randomization visit criteria

8. Adequate subject compliance with completion of an eDiary during the screening period;

9. Subjects with moderate or severe neuropathic pain as determined from daily entries of the modified BPI-SF3 score of “neuropathic pain at its worst in the last 24 hours” in the eDiary during the screening period.

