7.2.1.2 Data to be collected for screening failure subjects

- A minimal set of screening failure information is required to ensure transparent reporting of screening failure subjects.

For subjects who failed screening, the following data will be recorded in the eCRF:

- Age, sex, race, and ethnicity (if allowed in the country);
- Inclusion criteria not met and/or exclusion criteria met;
- FD history [see Section 7.2.1.1];
- FD-specific therapies [see Section 5.2.5.1];
- SAEs.

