10.3.5 Analysis of the safety variables

The SAF will be used to perform all safety analyses.

If not otherwise stated, only treatment-emergent safety data will be considered in tables and figures. All safety data will be included in listings, with flags for safety data not considered to be treatment-emergent.

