## **10 SAFETY VARIABLES**

For determination of treatment-emergent events, the safety analysis will retain the AEs with an onset date between the start of treatment date (included, provided that AE onset is not prior to first dose of study treatment, i.e., AE.AESTRTPT is different from BEFORE) and EOT + 30 days (included). AEs with missing or incomplete onset date compatible with being between the start of treatment date (included, provided that AE onset is not prior to first dose of study treatment, i.e., AE.AESTRTPT is different from BEFORE) and EOT + 30 days (included) will be considered treatment emergent.

For determination of treatment-emergent events, the safety analysis will retain the laboratory values, vital signs, and ECGs with a sampling or assessment date between the start of treatment date (excluded) and EOT + 30 days (included). The baseline value will be taken as the last value available up to the start of treatment date (included).

All laboratory, vital signs and ECG data are taken into account regardless of whether they correspond to scheduled or unscheduled assessments.

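### Non-fatal SAEs of screened but undosed subjects, including those who stopped ERT for the study, are collected but appear in no planned listing or table

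*SAP*

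**What the plan says.** **The risk and when it begins.** Protocol 1.4 includes among the potential risks of taking part "discontinuation of ERT [see Section 5.2.3.1"]. Under Protocol 4.3, criterion 5c, a subject on ERT qualifies only if: "Subject agrees to stop ERT administration at the screening visit for approximately 8 months". Protocol 3.1.1 says of the screening period: "Lasts approximately 6–7 weeks; starts with the signing of the informed consent form".

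**What is collected.** Protocol 7.2.1.2 states: "For subjects who failed screening, the following data will be recorded in the eCRF"; the list that follows includes SAEs. Its stated purpose is transparent reporting of these subjects. Protocol 9.3.2 requires every SAE after consent to go to the sponsor's drug safety department within 24 hours, whatever the causality.

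**What is tabulated.** Protocol 10.3.5 says that, unless otherwise stated, "only treatment-emergent safety data will be considered in tables and figures". SAP 10 sets the window: "the safety analysis will retain the AEs with an onset date between the start of treatment date" and 30 days after the end of treatment. The AE tables in SAP 16.1 are by treatment group.

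**What is listed.** SAP 16.1: "A listing of all SAEs will be prepared on the SAF". The same section prepares the listing of deaths on the SCR. SAP 4.1.6 defines the SAF as subjects with at least one dose; SAP 4.1.1 defines the SCR as all screened subjects with an identification number.

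**The concern.** Stopping ERT is required by the study, and it happens before the subject is known to be eligible. Diary compliance and the pain threshold (inclusion criteria 8 and 9) are judged at randomization from the 4 weeks before it, and ERT during screening is itself exclusionary (criterion 15). The design will therefore foreseeably produce some subjects who stop ERT and are then never dosed.

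If such a subject has a non-fatal cardiac, renal or cerebrovascular SAE, the event is recorded, but the SAP has no output in which it would appear. The protocol collects the information in order to report it, and the analysis plan gives it no place. The SAP does extend the deaths listing to all screened subjects, so the restriction applies only to non-fatal events.

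There is also a descriptive gap among treated subjects. Switch subjects in both arms stop ERT, so the comparison of lucerastat with placebo says nothing about the risk of stopping. Only a description by ERT status could, and the AE tables do not give one.

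**Working it through.** No stated figure is in dispute. The check sets each kind of SAE against the outputs that SAP 16.1 plans.

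| Subject and event | AE/SAE tables | SAE listing (SAF) | Deaths listing (SCR) |
|---|---|---|---|
| Treated, onset from first dose to end of treatment + 30 days | Yes, by arm | Yes | If fatal |
| Treated, onset between consent and first dose | No | Yes | If fatal |
| Randomized, never dosed, non-fatal | No | No | No |
| Screen failure, non-fatal | No | No | No |
| Never dosed or screen failure, fatal | No | No | Yes |

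The second row is covered because the listing is of all SAEs, not only treatment-emergent ones, and Protocol 10.3.5 puts all safety data into listings with the non-treatment-emergent items flagged. That sentence does not rescue rows three and four, because the same section makes the SAF the population for all safety analyses and SAP 16.1 repeats the SAF for this listing.

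**Grouping by ERT status.** The AE tables in SAP 16.1 are by arm, SOC, preferred term and, in places, intensity or relatedness. None is by ERT status at screening. The on-study SAP summary that is split this way and bears on stopping ERT is the count of ERT (re-)initiations (SAP 14.11).

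**Share of planned off-ERT time before first dose.** Inputs: screening of 42 to 49 days (Protocol Table 5); Month 6 at nominal Day 183 (SAP Table 5), with a visit window of Day 169 to Day 197 (Protocol Table 5). Formula: screening days / (screening days + Month 6 day).

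- 42 / (42 + 183) = 18.7%
- 49 / (49 + 183) = 21.1%
- Extremes of the window: 42 / (42 + 197) = 17.6% and 49 / (49 + 169) = 22.5%

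This is the share of planned time off ERT, up to Month 6, that lies outside every AE table. It is not the share outside the listings, since a treated subject's screening SAEs are listed.

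**Number affected.** The documents give neither the number of switch subjects who failed screening nor their SAEs, so no event count can be derived.

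**The case against.** A reader might infer that these SAEs are never reported, or that the trial cannot report harm from stopping ERT. The documents support neither. Every SAE after consent reaches the sponsor within 24 hours (Protocol 9.3.2), screen-failure SAEs are in the eCRF, the sponsor reviews safety data continuously (Protocol 9.6), an IDMC monitors safety (Protocol 3.3.1), and all deaths are listed on the SCR. ERT (re-)initiation is summarized by ERT status, and its date and detailed reason are recorded (Protocol 5.2.5.1). Saying that all non-fatal SAEs of screen failures are missing from the listing only restates the SAF definition; it measures nothing.

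It can also be argued that the safety objective concerns lucerastat, so tables by arm on treated subjects are the right ones. Pooling switch and naive subjects does not bias that comparison, because randomization is stratified by ERT status. Switch versus naive is not a randomized contrast, and with 118 subjects randomized, about 39 of them to placebo (SAP 2), SAE cells by arm within stratum would be sparse. The protocol also expects little worsening: it enrols subjects for whom continued ERT is judged not medically indicated and excludes those at high risk of organ involvement (Protocol 4.1, 4.4).

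Most of this stands, and it makes the tables by ERT status optional. It does not answer the listing gap. Submission to drug safety is not an output of this analysis plan, and an expectation of low risk is not a reason to leave recorded events out of the listing.

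**Conclusion.** The concern holds as a gap in planned reporting. If the SAP is followed as written, non-fatal SAEs of screen failures and of randomized but untreated subjects, including any who stopped ERT for the study, appear in no listing or table. For treated subjects the gap is smaller: screening-period SAEs are listed but not tabulated, which leaves about 19–21% of planned off-ERT time to Month 6 outside the tables (17.6–22.5% across the visit windows). AE tables also do not describe switch subjects separately.

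The consequence in events is unknown and may be small. The conclusion rests on reading the SAP literally and on no other unlisted output covering undosed subjects. It does not touch the efficacy analysis or the validity of the between-arm safety comparison.

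**What to change.** In SAP 16.1, prepare the listing of all SAEs on the SCR, as is already done for deaths, with flags for ERT status at screening, for screen failure or randomized-untreated status, and for onset before first dose.

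Optionally add two small descriptive tables: SAEs from consent to first dose (or screen failure) by ERT status, and treatment-emergent SAEs by arm within ERT stratum. State that they are descriptive only, because cells will be sparse and ERT status was not randomized; they cannot isolate the effect of stopping ERT.

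Two passages should be reconciled at the same time. Protocol 9.3.1 asks for all AEs after consent to be recorded, while 7.2.1.2 names only SAEs for screen failures, so the pre-dose table should be confined to SAEs. Protocol 1.4 points to Section 5.2.3.1 for ERT discontinuation, but that section covers ACE inhibitors and ARBs; ERT is in 5.2.4.1.

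The cost is SAP wording, one change of listing population and slightly more output. The required data are already collected, and alpha, power and sample size do not change. No change to clinical management is proposed.

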## 16.2 Laboratory data

### 16.2.1 Change from baseline to each visit up to Month 6

For quantitative parameters, summaries of the observed value and change from baseline at each visit will be presented by treatment group, using the windowed times as described in [Table 15](#). For categorical parameters (e.g., proteinuria), shift tables reflecting change from baseline will be presented by treatment group at each visit, using the windowed times as described in [Table 15](#). Results of male reproductive hormones and of semen analyses will be listed.

**Table 15 Time windows for all assessments up to EOT + 30 days**

Visit	Treatment day (nominal value)	Lower limit treatment day	Upper limit treatment day
Month 1	30	2	45
Month 2	61	46	75
Month 3	91	76	106
Month 4	122	107	136
Month 5	152	137	167
Month 6	183	168	EOT + 30

Should more than one assessment fall within the same time window, then the closest value to the planned treatment day will be assigned to the visit. In the event of values that are equidistant to the planned treatment day, the latest assessment will be retained.

Where more than one assessment falls on the same day, the first available central assessment is used.

### 16.2.2 Treatment-emergent marked abnormalities

The number and percentage of subjects with treatment-emergent marked laboratory abnormalities will be tabulated by treatment group for each laboratory parameter for which marked abnormalities are defined in [Table 16](#), [Table 17](#) and [Table 18](#). For a given parameter, percentages will be based on the number of subjects at risk: those not meeting

the criterion at baseline (or having a missing baseline value) and having at least one post-baseline value (not later than EOT + 30).

Marked abnormalities are classified as high (HH, HHH, HHHH flags) or low (LL, LLL, LLLL flags) based on values occurring above the higher limit or below the lower limit, respectively. It is possible that, for a given parameter, the same subject is counted as a high marked abnormality for an observed value and as a low marked abnormality for a different observed value. Only the most severe abnormality will be counted (e.g., a subject meeting the “HHH” criterion for a specific laboratory parameter will not be summarized under “HH” for this parameter).

**Table 16**      **Marked abnormalities for hematology**

Variable	Abnormality
Hemoglobin (g/L)	< 80 (LLL flag) < 100 (LL flag) > 20 above ULN or > 20 above baseline if baseline > ULN (HH flag) > 40 above ULN or > 40 above baseline if baseline > ULN (HHH flag)
Leukocytes (10  /L)	< 2.0 (LLL flag) < 3.0 (LL flag) > 20.0 (HH flag) > 100.0 (HHH flag)
Neutrophils (10  /L)	< 1.0 (LLL flag) < 1.5 (LL flag)
Lymphocytes (10  /L)	< 0.5 (LLL flag) < 0.8 (LL flag) > 4.0 (HH flag) > 20.0 (HHH flag)
Eosinophils (10  /L)	> 5.0 (HH flag)
Platelets (10  /L)	< 50 (LLL flag) < 75 (LL flag) > 600 (HH flag) > 999 (HHH flag)

ULN = upper limit of normal range.

**Table 18**      **Marked abnormalities for urinalysis (dipstick analysis)**

Variable	Abnormality
Bilirubin	3+ (HH flag)
Occult blood	3+ (HH flag)
Glucose	3+ (HH flag)
Ketones	3+ (HH flag)
Leukocyte esterase	3+ (HH flag)
Protein	3+ (HH flag)

Patient listings will also flag values without marked abnormalities but outside of the normal range as H (high; LB.LBNRIND = HIGH) or L (low; LB.LBNRIND = LOW). Results with LB.LBSTRESC available as < x.x (below x.x) will be displayed as < x.x in the patient listing but analyzed as x.x (equal to x.x). Results with LB.LBSTRESC available as > x.x (above x.x) will be displayed as > x.x in the patient listing but analyzed as x.x (equal to x.x).

Semen analysis data will be listed with a flag (L) for sperm concentrations corresponding to a decrease from baseline of 50% or more.

